5.8 Subject Withdrawal/Discontinuation Criteria

Subjects may withdraw consent at any time for any reason or be dropped from the trial at the discretion of the investigator should any untoward effect occur. In addition, a subject may be withdrawn by the investigator or the Sponsor if enrollment into the trial is inappropriate, the trial plan is violated, or for administrative and/or other safety reasons. Specific details regarding discontinuation or withdrawal are provided in Section 7.1.3 – Other Procedures.

A subject must be discontinued from the trial for any of the following reasons:

- The subject or legal representative (such as a parent or legal guardian) withdraws consent.
- Confirmed radiographic disease progression

Note: For unconfirmed radiographic disease progression, please see Section 5.2.2

Note: A subject may be granted an exception to continue on treatment with confirmed radiographic progression if clinically stable or clinically improved, please see Section 7.1.2.7.1

- Unacceptable adverse experiences as described in Section 5.2.1.2
- Intercurrent illness that prevents further administration of treatment
- Investigator's decision to withdraw the subject
- The subject has a confirmed positive serum pregnancy test
- Noncompliance with trial treatment or procedure requirements
- The subject is lost to follow-up
- Completed 24 months of treatment with MK-3475

Note: 24 months of study medication is calculated from the date of first dose. Subjects who stop MK-3475 after 24 months may be eligible for up to one year of additional study treatment if they progress after stopping study treatment provided they meet the requirements detailed in Section 7.1.5.2.1.

- Administrative reasons

The End of Treatment and Follow-up visit procedures are listed in Section 6 (Protocol Flow Chart) and Section 7.1.5 (Visit Requirements). After the end of treatment, each subject will be followed for 30 days for adverse event monitoring (serious adverse events will be collected for 90 days after the end of treatment as described in Section 7.2.3.1). Subjects who discontinue for reasons other than progressive disease will have post-treatment follow-up for

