9.1 Data Set Descriptions

This study will utilize a standard 3+3 design and dose de-escalation will proceed according to the following scheme. Three doses of MK-3475 (100 mg, 150 mg, 200 mg) will be given to 3 different groups of 3 patients. If the toxicity is greater than 1/3 in one group then the next lower dose will be used. This will establish the MTD, if present. If more than 1/3 of patients experience DLTs at the lowest dose (70 mg), it will be concluded that MK-3475 cannot be given safely with chemo/radiation. If one of three patients at any dose level experiences grade 3 or greater toxicity then another 3 patient will be accrued at the same dose level. If 1/6 patients has grade 3 or higher toxicity then escalation will proceed, if 2/6 has grade 3 or greater toxicity then this is declared the MTD. If 3/6 has grade 3 or greater then we will reduce the dose level.

Part A: Is only for patients with Limited stage SCLC, we will allow induction chemotherapy.

Part A for LS-SCLC

Part B: Is only for patients with Extensive stage SCLC who are receiving consolidation XRT after 1-6 cycles of chemotherapy.

[figure not shown]

Table 1: Dose De-escalation, For Part A and B

Dose Level	MK-3475 (dose during XRT)	Toxicity Assessment	New MK 3475 dose
+2	200mg Q 3 weeks	If over 1/3 grade 3 toxicity is seen	150mg Q 3 weeks
+1	150mg Q 3 weeks	If over 1/3 grade 3 toxicity is seen If 0/3 grade 3 toxicity is seen	100mg Q 3 weeks 200mg Q 3 weeks
0 (starting dose)	100mg Q 3 weeks	If over 1/3 grade 3 toxicity is seen If 0/3 grade 3 toxicity is seen	70mg Q 3 weeks 150mg Q3 weeks
-1	70mg Q 3 weeks	If over 1/3 grade 3 toxicity is seen	We will conclude MK-3475 cannot be safely given after Chemo/radiation

Once the MTD is determined for each study part we will accrue at this MTD until we reach a total of 40 patients for each study part. Should DLTs occur in more than 1/3 of patients enrolled into this expanded cohort, dosing at that level will be stopped. A review of all DLTs observed will be conducted, and the need to lower the dose will be based on the discussion and agreement between

the IRB and the Investigator. Once at dose level +2, if 0/3 toxicity is seen we will not close the study for new patient enrollment until the third patient has passed the DLT assessment period, because even if this third patient has a DLT was seen it would no change the dose for future patients as another 3 patients at the same dose level would be needed.

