All patients who receive any MK-3475 will be considered evaluable for response and will be included in the efficacy data set.

DLT is defined as any:

- DLTs are defined as any adverse event(s) considered related to the combination of MK-3475 plus radiation as described below:
 - Any \geq Grade 3 bronchospasm or other hypersensitivity reaction;
 - Any other \geq Grade 3 non-skin related adverse event with the exception of laboratory abnormalities;
 - Any Grade 4 laboratory abnormalities, except AST, ALT, or total bilirubin;
 - AST or ALT $> 8 \times$ ULN,
 - Total bilirubin $> 5 \times$ ULN;
 - Any other Grade 4 adverse event;
- 1. Any adverse event, laboratory abnormality or intercurrent illness which, in the judgment of the investigator, presents a substantial clinical risk to the subject with continued study drug dosing;
- 2. Subject experiences an allergic/infusion reaction while receiving study drug at a slower infusion rate due to a prior allergic/infusion reaction;
- 3. Any motor neurologic toxicity \geq Grade 3 regardless of causality;
- 4. Any \geq Grade 3 treatment-related sensory neurologic toxicity.
- 5. Drug related toxicity that prevents administration of MK-3475 for > 21 days from the scheduled dose
 - The time frame for DLT assessment will be within 22 days of therapy initiation.
 - Any grade 4 neutropenia (with or without fever and/or sepsis) or thrombocytopenia (with or without bleeding) lasting at least 1 week or longer (as defined by the NCI-CTC v4.0).
 - Any other grade 3 non-hematologic toxicity including symptoms/signs of vascular leak or cytokine release syndrome; or any severe or life-threatening complication or abnormality not defined in the NCI-CTCAE v4.0 that is attributable to the therapy.

9.2.1. *Statistical Analysis*

Descriptive statistics will be computed for all relevant outcomes, including toxicity, tumor response, PFS, OS, and biomarker response. Descriptive analysis will include a global assessment of patient outcomes for parts A and B separately. All patients receiving at least 1 treatment with MK-3475 will be included in the analysis.

9.2.2. *Demographics and Baseline Characteristics*

Frequency distributions of gender and race will be tabulated by dose/cohort. Summary statistics for age, body weight, height, and Body Mass Index (BMI) will be tabulated by dose/cohort.

9.2.3. *Safety Analyses*

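### Section 9.1 sets the MTD by counting two different things, grade 3 toxicity and DLTs, and DLT item 5 matures only after the 22-day window

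*Combined protocol and SAP*

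**What the plan says.** Section 9.1 describes a standard 3+3 design with MK-3475 at 70, 100, 150 or 200 mg every 3 weeks; Section 9.0 says that it runs independently in Parts A and B. The rules are worded as follows.

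- **Cohort rules (text).** Three more patients are added "If one of three patients at any dose level experiences grade 3 or greater toxicity". With six patients, one event means escalate, two means that the level is the MTD, and three means reduce. Each is stated as grade 3 or greater (or higher) toxicity. A general sentence before them lowers the dose when toxicity, with no grade given, exceeds 1/3 in a group.
- **Table 1 of Section 9.1.** All four dose levels, 70 mg included, carry the trigger "If over 1/3 grade 3 toxicity is seen".
- **70 mg (text).** The rule begins "If more than 1/3 of patients experience DLTs at the lowest dose (70 mg" and ends in the conclusion that MK-3475 cannot be given safely with chemo/radiation.
- **Expansion.** "Should DLTs occur in more than 1/3 of patients enrolled into this expanded cohort, dosing at that level will be stopped".
- **Level +2.** The sentence on keeping enrollment open speaks of a DLT in the third patient as the event that leads to three more patients, and refers to a DLT assessment period.

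The DLT list after Table 1 opens by requiring a relation to MK-3475 plus radiation. Item 5 is "Drug related toxicity that prevents administration of MK-3475 for > 21 days from the scheduled dose". The line after it sets the window: "The time frame for DLT assessment will be within 22 days of therapy initiation". For neutropenia the list has "Any grade 4 neutropenia (with or without fever and/or sepsis) or thrombocytopenia (with or without bleeding) lasting at least 1 week or longer"; a separate bullet takes any grade 4 laboratory abnormality except AST, ALT and total bilirubin, with no duration.

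**The concern.** Safety is the primary objective (Section 3.1), the MTD is the stated purpose of the primary endpoint (Section 4.2.3.1), and the MTD fixes the dose at which each part accrues up to 40 patients. A 3+3 rule acts on single events, so the event must be defined once. Here the same patient can count under one sentence and not under another, and two careful readers could declare different MTDs from the same data. Attribution matters most in Part A, where Section 8.0 gives platinum and etoposide concurrently: a grade 3 event put down to chemotherapy alone counts under the cohort rules but generally not as a DLT.

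The second matter is one of timing. Item 5 describes a delay longer than three weeks in a dose that is itself not due until three weeks after the first, yet assessment is limited to 22 days.

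**Working it through.** **1. Which unit each rule counts**

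| Rule in Section 9.1 | Unit | Attribution or window in the rule |
|---|---|---|
| 1/3, 1/6, 2/6, 3/6 (text) | grade 3 or greater toxicity | none |
| Table 1, all rows | grade 3 toxicity | none |
| 70 mg (text) | DLT | through the DLT list |
| Expansion, more than 1/3 | DLT | through the DLT list |
| Level +2 | DLT | refers to the DLT assessment period |

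At 70 mg the text and Table 1 reach the same conclusion from different units.

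**2. Whether the units coincide**

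- *Grade 3 but not a listed DLT.* Uncomplicated grade 3 neutropenia. One clause takes grade 3 events but excepts skin events and laboratory abnormalities; the last bullet takes other grade 3 toxicity only if non-hematologic; both entries that cover neutropenia need grade 4. The two grade 4 entries differ on duration, but that does not touch this example. Non-hematologic grade 3 laboratory events are a less clean example, because the last bullet arguably brings them back in.
- *DLT but below grade 3.* Item 1 (investigator's judgment of substantial risk), item 2 (reaction at a slowed infusion rate) and item 5 have no grade 3 threshold.
- *Attribution.* The lead-in requires relation to MK-3475 plus radiation; motor neurologic toxicity is the stated exception. The cohort rules require none.

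**3. What one event does**

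| Count | Becomes | Decision changes from | to |
|---|---|---|---|
| 0/3 | 1/3 | escalate | add 3 patients |
| 1/3 | 2/3 | add 3 patients | lower dose |
| 1/6 | 2/6 | escalate | MTD |
| 2/6 | 3/6 | MTD | lower dose |

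This is a boundary effect: 2/3 to 3/3 and 3/6 to 4/6 change nothing.

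**4. Illustration only**

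Let p be the per-patient rate of whatever is counted. Under the text rules, P(escalate) = (1 − p)³ + 3p(1 − p)⁵.

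- p = 0.10: 0.729 + 0.177 = 0.906
- p = 0.20: 0.512 + 0.197 = 0.709
- p = 0.30: 0.343 + 0.151 = 0.494

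The documents give neither a DLT rate nor an all-cause grade 3 rate, so these values of p are assumptions. They show only that the outcome depends on which event is counted.

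**5. When item 5 can first be true**

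Inputs: dosing every 3 weeks (Section 5.2, Table 2; Section 9.1, Table 1); more than 21 days from the scheduled dose (item 5); a 22-day window; ±3 days for administration (Section 5.2.2). Day 1 is taken as the first MK-3475 dose.

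- Dose 2 due: Day 1 + 21 = Day 22.
- More than 21 days late, first whole day: Day 22 + 22 = Day 44.
- After the window: 44 − 22 = 22 days.
- With dose 2 set 3 days earlier or later (Day 19 or Day 25): Day 41 or Day 47.

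The plan does not define therapy initiation. The nearest text is Section 5.8, on treatment duration: "24 months of study medication is calculated from the date of first dose". If chemotherapy or radiation begins first and starts the clock, the gap widens. Counting the delay from the Day 1 dose gives Day 23, still outside unless Day 1 is numbered 0, and does not fit a criterion about a prevented dose.

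**The case against.** The best defense of the cohort rules is that grade 3 toxicity is shorthand for DLT. The design is called a standard 3+3, and the level +2 sentence uses DLT for the same add-three rule and ties it to an assessment period. That may well be what is meant, and it weakens any claim that the cohort rules were intended to have no window. It does not settle the matter: no sentence equates the terms, and Table 1, the natural place to look during the trial, uses grade 3 toxicity in every row.

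On item 5, a reader might infer that the criterion can never be met. That holds only if the window limits assessment in the strict sense. If it limits onset, a toxicity that starts by Day 22 can satisfy item 5 later, and what is missing is an instruction to defer the cohort decision. The visible text has none; the trial diagrams are not in the copy reviewed. Item 1 can also catch some of these events at once. What stands is narrow: patients whose second dose is held for drug-related toxicity and whose event is not already a DLT under another item. Such holds are foreseen, mainly at grade 2 (Table 3 in Section 5.2.1.2; enterocolitis in Section 5.6.1; pneumonitis, up to 12 weeks, in Section 5.6.1.2).

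A reader might also infer that toxicity after Day 22 is ignored. The documents do not support that. Events of clinical interest are reported to 90 days after treatment (Section 7.2.3.2), adverse events are tabulated by dose (Section 9.2.3), and Section 5.10 allows early termination. Whether late events enter the expansion count follows from how the window is read, so it is not a separate gap.

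**Conclusion.** The inconsistency is real and should be fixed. The rules that set the MTD use two units that differ in both directions, and at 70 mg one conclusion is stated both ways. This rests on the wording alone and needs no assumed rate.

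Its size is one step of a cohort decision, when a patient has an event that counts under only one unit and the cohort is at a boundary. It would go too far to infer that the trial is likely to declare a wrong MTD: the documents give no rate for such events and do not show which unit is intended.

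The item 5 conflict is secondary and less certain. The date of about Day 44 assumes that therapy initiation is the first MK-3475 dose; the consequence depends on whether the window means assessment or onset.

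**What to change.** Reconcile the rules with the DLT list; which rule to keep is the sponsor's choice.

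1. Use one defined term, with its attribution and window, in the cohort rules, the 70 mg sentence, all rows of Table 1, the level +2 sentence and the expansion rule.
2. Define therapy initiation and make item 5 and the 22-day window compatible. One way is to state that the window refers to onset and that the cohort decision waits for a patient whose second dose is being held for drug-related toxicity; another is to amend the window or the item.

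The cost is wording, with no new data. If the sponsor chooses to wait for item 5, the delay is at most 22 days and only in cohorts with a held second dose. At the 1.5 patients per month in Section 9.2.5 (read as per part, since 1.5 × 26 months = 39, close to 40), that is 1.5 × 22/30.4 = 1.1 patients.

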4.2.3 Rationale for Endpoints

4.2.3.1 Efficacy Endpoints

Part A LS-SCLC: The primary endpoint is safety in order to establish the MTD of MK-3475 with concurrent chemo and radiation. The primary acute toxicity for chemo and radiation is esophagitis with a rate of $\geq 32\%$ ⁸. While the long term toxicity rate of grade 3 pneumonitis is around 13%⁹.

Part B ES-SCLC: The primary endpoint is safety in order to establish the MTD of MK-3475 with concurrent radiation. The primary acute toxicity for chemo and radiation is esophagitis with a rate of $\geq 32\%$ ⁸. While the long term toxicity rate of grade 3 pneumonitis is around 13%⁹.

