5.2.1 Dose Selection/Modification

5.2.1.1 Dose Selection

The rationale for selection of doses to be used in this trial is provided in Section 4.0 – Background and Rationale.

The dose amount required to prepare the MK-3475 infusion solution will be based on the dose level which a patient is being treated on as per table 1.

Radiation will be given as per our institutional standard. For the patient in the LS-SCLC arm we will use 45Gy delivered BID over 15 days (we will allow a GTV boost to 54Gy, as long as the PTV dose remains at 45Gy). For patients with ES-SCLC we will use a dose of 45Gy daily (we will allow at GTV boost dose to 52.5Gy, as long as the PTV dose remains at 45Gy).

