Subjects should be assessed for possible ECIs prior to each dose. Lab results should be evaluated and subjects should be asked for signs and symptoms suggestive of an immune-related event. Subjects who develop an ECI thought to be immune-related should have additional testing to rule out other etiologic causes. If lab results or symptoms indicate a possible immune-related ECI, then additional testing should be performed to rule out other etiologic causes. If no other cause is found, then it is assumed to be immune-related.

ECIs that occur in any subject from the date of first dose through 90 days following cessation of treatment, or the initiation of a new anticancer therapy, whichever is earlier, whether or not related to the Merck’s product, must be reported within 24 hours to the Sponsor and to Merck Global Safety within 2 working days.

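### The 22-day DLT window leaves later pneumonitis, which the protocol itself calls long-term, without weight in the expansion limit and possibly in the cohort tallies that set the MTD

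*Combined protocol and SAP*

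**What the plan says.** **Endpoint.** For Part A, Section 4.2.3.1 says: "The primary endpoint is safety in order to establish the MTD of MK-3475 with concurrent chemo and radiation". Part B has the matching aim with radiation alone. The section names the same two toxicities for each part: "The primary acute toxicity for chemo and radiation is esophagitis with a rate of" at least 32%, and "While the long term toxicity rate of grade 3 pneumonitis is around 13" percent. It gives no onset time for either.

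**Window.** Among the DLT definitions in Section 9.1: "The time frame for DLT assessment will be within 22 days of therapy initiation". Which therapy starts the clock is not stated. Item 5 of the same list makes a DLT of any drug-related toxicity that holds up MK-3475 by more than 21 days past a scheduled dose.

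**Decision rules (Section 9.1).** The 3+3 sentences and Table 1 count toxicity of grade 3 or above and mention no window. The text on dose level +2 does refer to patients completing a DLT assessment period. The expansion limit is written in DLTs: "Should DLTs occur in more than 1/3 of patients enrolled into this expanded cohort, dosing at that level will be stopped".

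**Radiation (Section 5.2.1.1).** Part A: "For the patient in the LS-SCLC arm we will use 45Gy delivered BID over 15 days". Part B: "For patients with ES-SCLC we will use a dose of 45Gy daily", with no number of fractions.

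**Other safety provisions.** All adverse events are recorded to 30 days after treatment (Section 7.2), and SAEs to 90 days (7.2.3.1). Pneumonitis of grade 2 or above is an expedited event of clinical interest, and the reporting duty covers "ECIs that occur in any subject from the date of first dose through 90 days following cessation of treatment" (7.2.3.2), ending earlier if new anticancer therapy begins. Adverse events are tabulated by grade, type and dose (9.2.3). Section 5.10 allows early termination if the incidence or severity of adverse reactions suggests a hazard.

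**The concern.** The trial's main product is an MTD for MK-3475 given with radiation. One of the two toxicities that the protocol names for that purpose is, by its own label, long-term, while the rules that fix and police the MTD look at about one three-week cycle out of 16 planned. A related grade 3 or 4 pneumonitis at week 6 requires MK-3475 to be discontinued under Table 7 (Section 5.6.1.2), yet it would not count toward the expansion limit. Whether it counts in a cohort tally depends on which sentence of Section 9.1 is followed. If the window governs throughout, the declared MTD describes tolerance up to about the end of radiation, and the only numerical limit in the expansion cannot react to what happens afterwards.

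**Working it through.** The plan gives no operating characteristic for the window or the expansion limit. Its one safety probability (88%, Section 9.2.5) does not bear on this point.

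**1. Window against radiation.** Assume radiation and MK-3475 both start on day 1, with five treatment days a week.
- Part A, 15 weekdays: the last fraction falls on day 19 (Monday start) or day 21 (other weekdays). The window closes 22 − 21 = 1 to 22 − 19 = 3 days later. If the 15 days are calendar days, it closes 7 days later.
- Part B, fraction size assumed because none is stated. At most 16 weekday fractions fit by day 22.

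| Assumed Gy per fraction | Fractions for 45 Gy | Last fraction, day |
|---|---|---|
| 3.0 | 15 | 19–21 |
| 2.5 | 18 | 24–26 |
| 2.0 | 22.5, taken as 23 | 31–33 |
| 1.8 | 25 | 33–35 |

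So in Part B the window closes either about when radiation ends or up to 35 − 22 = 13 days before. If radiation starts after the clock does, less of it is covered in either part.

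**2. Window against DLT item 5.** With dosing every 3 weeks, dose 2 is due on day 22. A delay of more than 21 days is first known on day 22 + 22 = 44. For dose 2, item 5 cannot be met inside the window.

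**3. Expansion limit.** Inputs: 40 patients per part, less three cohorts of three, leaves 40 − 9 = 31 expansion patients (an assumption; larger cohorts leave fewer). More than 1/3 of 31 means 11 or more. Let r be the true rate of qualifying pneumonitis and f the share arising by day 22. Neither f nor any r other than 13% is in the documents. Then P = P(X ≥ 11), X ~ Binomial(31, r·f), for pneumonitis alone.

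| r | f | r·f | P(limit crossed) |
|---|---|---|---|
| 13% | 1 | 0.13 | 0.1% |
| 26% | 1 | 0.26 | 16% |
| 40% | 1 | 0.40 | 75% |
| 40% | 0.75 | 0.30 | 31% |
| 40% | 0.5 | 0.20 | 3% |
| 40% | 0.1 | 0.04 | <0.01% |

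Applying the limit to all 40 patients (14 or more) gives 79% and 1.9% at r = 40% with f = 1 and 0.5, so the pattern does not hinge on 31.

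**4. Cohort tallies, if the window governs them.** P(escalate past one level) = (1 − p)³ + 3p(1 − p)² × (1 − p)³, with p = r·f.
- r = 13%: 85% at f = 1, 96% at f = 0.5, 99% at f = 0.25.
- r = 40%: 31% at f = 1, 71% at f = 0.5, 91% at f = 0.25, 98% at f = 0.1.

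**5. A longer count under the same limit.** Treat the background rates in Section 4.2.3.1 as independent, all qualifying and all attributed to the combination: 1 − (1 − 0.32)(1 − 0.13) = 0.408. Then P(X ≥ 11 of 31) = 78% with no added drug effect. This is an extreme case, since the grade of the 32% is not stated and attribution would remove some events.

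**The case against.** **Late pneumonitis is not invisible.** It is collected, expedited and tabulated, and Section 5.10 lets the trial be terminated for it. Escalation patients have the same follow-up as expansion patients. This stands: the gap is in the decision rules, not in surveillance. A reader might infer that nothing could stop a trial with heavy late pneumonitis; the documents do not support that. They show only that no provision outside the DLT rules has a threshold or sets the MTD.

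**Section 9.1 is not settled.** Its 3+3 sentences carry no window, so a week-6 event might count in a cohort. This also stands. The loss of weight is clear for the expansion limit, which is written in DLTs, and conditional for the cohort tallies.

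**Esophagitis.** A reader might infer that both named toxicities largely escape the window. The protocol calls esophagitis acute and gives no onset time, and related grade 3 events during radiation would be DLTs. Only an unknown share that arises later would be missed.

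**The figures are chosen.** The 75% contrast needs a true rate about three times the protocol's 13%. At twice that rate, even full counting crosses the limit only 16% of the time. This is a fair limit on the size claimed.

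**A short window has a purpose.** Waiting for late events before each cohort would slow escalation. That supports 22 days for opening cohorts, but not for confirming the MTD or policing the expansion.

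**Conclusion.** The point holds for pneumonitis. The protocol ties its primary endpoint to a toxicity that it calls long-term, and then closes DLT assessment at day 22 of an undefined clock. Later related pneumonitis carries no weight in the expansion limit and, if the window governs the 3+3 sentences, none in the cohort tallies. The same window cannot accommodate item 5 for the second dose.

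The size cannot be fixed from the documents, because the share of events arising by day 22 is unknown. If none arise by then, pneumonitis contributes nothing to any rule bound by the window, whatever its true rate. At an assumed 40% rate, a half share already cuts the chance of crossing the limit from 75% to about 3%. At 13% to 26% the limit is seldom crossed by pneumonitis alone even with full counting, so the 1/3 limit itself also needs examination.

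The Part A timing assumes a same-day start and weekday treatment. A reader might infer that Part B radiation always outlasts the window; with no fraction count, that is possible but not established.

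**What to change.** Reconcile Sections 4.2.3.1 and 9.1, as a wording change to the protocol and its analysis plan:

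1. State that the 22-day window governs only the opening of the next cohort, and whether the unwindowed 3+3 sentences and Table 1 mean DLTs.
2. For confirming the MTD and for the expansion limit, also count later events that meet the DLT definition and are judged related to the combination. At a minimum these are pneumonitis of grade 3 or above and item 5 delays. Use the follow-up already collected: SAEs and events of clinical interest to 90 days after treatment, other adverse events to 30 days. Update the tallies as events arrive.
3. Define the start of the clock so that events between the first MK-3475 dose and the start of radiation, such as a hypersensitivity reaction to the first infusion, still count.
4. State the Part B fraction count, so that the window can be placed against the course.
5. Give the operating characteristics of the 1/3 limit under the longer count, over a range of true rates and attribution, because background toxicity alone could approach it.
6. Report grade 3 or higher pneumonitis and esophagitis by dose level beside the 22-day DLT rate, over the period for which each is collected.

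The pneumonitis count needs no new data. Non-serious esophagitis is not on the Section 7.2.3.2 list and is recorded only to 30 days after treatment, so a 90-day figure should not be promised for it. The costs are that the MTD may be revised after expansion has begun and that the expansion limit may be crossed more often.

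### The DLT list both exempts and counts grade 3 skin events, and the dose rules name their trigger in three ways without saying which governs

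*Combined protocol and SAP*

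**What the plan says.** Section 9.1 of the combined protocol and SAP holds both the DLT definition and the dose rules.

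The DLT list opens with an attribution condition: "DLTs are defined as any adverse event(s) considered related to the combination of MK-3475 plus radiation as described below". The items that matter here are:

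- First item: hypersensitivity reactions of grade 3 or higher count.
- Second item, from grade 3 upward: any other "Grade 3 non-skin related adverse event with the exception of laboratory abnormalities".
- Third item: "Any Grade 4 laboratory abnormalities, except AST, ALT, or total bilirubin". Separate limits follow, at 8 times ULN for AST or ALT and 5 times ULN for total bilirubin.
- A grade 4 catch-all: "Any other Grade 4 adverse event".
- Near the end: grade 4 neutropenia or thrombocytopenia that lasts a week or more.
- Last item: "Any other grade 3 non-hematologic toxicity including symptoms/signs of vascular leak or cytokine release syndrome".

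The assessment window is 22 days from the start of therapy.

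The dose rules name the trigger differently from place to place. The cohort rule reads "If one of three patients at any dose level experiences grade 3 or greater toxicity", in which case three more patients enter. The 1/6 (escalate), 2/6 (MTD) and 3/6 (reduce) rules are also stated in terms of toxicity at grade 3 or above. Table 1 uses "If over 1/3 grade 3 toxicity is seen". At 70 mg its consequence is "We will conclude MK-3475 cannot be safely given after Chemo/radiation", yet the text states the same 70 mg conclusion in terms of DLTs. The expansion stop is also stated in DLTs. One earlier sentence refers to toxicity with no grade at all.

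**The concern.** The primary aim is the MTD in each part, and the DLT count decides it. If the list gives two answers for the same event, two readers can take different dose decisions from the same data. The event is foreseeable: Section 3.9 of the guidance in Appendix 13.4 makes grade 3 rash reportable for this drug, although it gives no frequency.

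The trigger wording adds a second uncertainty. Read literally, grade 3 toxicity is wider than the DLT list. It would take in uncomplicated grade 3 cytopenias and events not attributed to MK-3475 plus radiation, most of which the list leaves out. That would matter chiefly in Part A, where Section 8.0 gives every patient platinum and etoposide.

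**Working it through.** No sample size or probability stated in the plan depends on this wording, so there is no figure to reproduce. The check is a reading of the text, followed by an illustration.

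**Step 1. Skin events, item by item.** Take a related skin event that is not a hypersensitivity reaction.

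| Grade | Second item | Grade 4 catch-all | Last item |
|---|---|---|---|
| 3 | exempt | not reached | counts |
| 4 | exempt | counts | not reached |
| 5 | exempt | names grade 4 only | names grade 3 only |

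The conflict is at grade 3. At grade 5 the literal list has a gap.

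**Step 2. Laboratory values.** The second item exempts laboratory abnormalities, and the list sets its own liver limits (8 and 5 times ULN). Section 3.5 of the Appendix 13.4 guidance puts its grade 3 action thresholds at AST/ALT above 5.0 and bilirubin above 3.0 times ULN. Values of 5-8 and 3-5 times ULN are therefore below the list's limits, but the last item would catch them if chemistry values are non-hematologic toxicity. Sections 5.2.1.2 and 8.3.2.3 class them that way, but those are dose-modification rules and do not define a DLT. This overlap is an inference.

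**Step 3. What one patient can change.** From the Section 9.1 rules, one extra scored patient turns:

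- 0/3 into 1/3: three more patients instead of escalation
- 1/3 into 2/3: reduce instead of three more patients
- 1/6 into 2/6: MTD declared instead of escalation
- 2/6 into 3/6: reduce instead of MTD

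**Step 4. Illustration with assumed rates.** The documents give no 22-day DLT rate and no grade 3 skin rate. Section 4.2.3.1 gives acute esophagitis at 32% or more (grade unstated) and long-term grade 3 pneumonitis at about 13%; neither is a 22-day DLT rate. Base risks of 15%, 20% and 32% are therefore assumed, with disputed events (skin, and possibly chemistry) added independently at 2%, 5% or 10%.

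Combined risk: p = 1 − (1 − base)(1 − added). For one dose level:

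- P(0/3) = (1 − p)³ and P(1/3) = 3p(1 − p)²
- Escalate = P(0/3) + P(1/3) × P(0/3)
- MTD = P(1/3)²
- Reduce = 1 − escalate − MTD

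Worked case, p = 0.15: P(0/3) = 0.85³ = 0.6141 and P(1/3) = 3 × 0.15 × 0.85² = 0.3251. Escalate = 0.6141 + 0.3251 × 0.6141 = 0.8138, MTD = 0.3251² = 0.1057, reduce = 0.0805.

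| Base | Added | p | Escalate | MTD | Reduce |
|---|---|---|---|---|---|
| 15% | 0 | 0.150 | 0.8138 | 0.1057 | 0.0805 |
| 15% | 2% | 0.167 | 0.7789 | 0.1209 | 0.1002 |
| 15% | 5% | 0.1925 | 0.7248 | 0.1418 | 0.1334 |
| 15% | 10% | 0.235 | 0.6324 | 0.1702 | 0.1974 |
| 20% | 0 | 0.200 | 0.7086 | 0.1475 | 0.1439 |
| 20% | 5% | 0.240 | 0.6215 | 0.1729 | 0.2055 |
| 20% | 10% | 0.280 | 0.5358 | 0.1896 | 0.2746 |
| 32% | 0 | 0.320 | 0.4540 | 0.1971 | 0.3489 |
| 32% | 5% | 0.354 | 0.3891 | 0.1964 | 0.4145 |
| 32% | 10% | 0.388 | 0.3292 | 0.1901 | 0.4808 |

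At 70 mg, reducing means concluding that the drug cannot be given.

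**Step 5. Secondary figures.** Expansion stop, only if the MTD is 200 mg and with one final look: between 40 − 18 = 22 and 40 − 9 = 31 patients remain, and more than 1/3 means at least 8 of 22 or 11 of 31. At base 15%, adding 5% or 10% moves the chance of crossing from 1.1% to 4.6% or 12.3% (22 patients), and from 0.4% to 2.5% or 9.0% (31 patients).

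Part A under the literal trigger: at base 15%, suppose 20% or 40% of patients have an uncomplicated grade 3 cytopenia or an unattributed grade 3 event. Then p = 0.32 or 0.49, and the chance of escalating falls from 81% to 45% or 18%. Those two added rates are pure assumptions.

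**The case against.** The list can be read as one coherent scheme: non-skin events from grade 3, laboratory values from grade 4 with specific liver limits, then residual catch-alls. On that reading the words *any other* in the last item leave the earlier exceptions intact. This is possible, and it has the merit of giving every exception some work to do. But the text does not say it, and *any other* just as naturally reaches whatever has not yet been counted. The skin conflict stands.

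The trigger wording may be mere shorthand. Section 9.1 declares a standard 3+3 design, its sentence on level +2 uses toxicity and DLT for the same count, and the 70 mg conclusion appears in both forms. This objection largely succeeds: the terms are probably synonyms. What remains is that no sentence says so.

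The layout of the list may have been lost in the PDF. The last item appears beneath numbered item 5, so whether the attribution condition governs it cannot be seen. That limits certainty but does not remove the skin conflict.

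Finally, numbered item 1 lets the investigator call a DLT for any event judged a substantial risk. That holds under every reading, but it does not settle how an ordinary grade 3 rash is scored.

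**Conclusion.** The list conflicts on related grade 3 skin events that are not hypersensitivity reactions. The overlap for liver chemistry is possible but depends on how chemistry values are classed. The trigger terms are unaligned but probably meant as one. This is an inconsistency in a stated decision rule, it should be fixed, and the fix is cheap.

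Size, on assumed and independent rates: with a 15% base risk and 2%, 5% or 10% disputed events, the chance of escalating falls from 81% to 78%, 72% or 63%. At the low end the effect is small. The textual conflict does not depend on these rates.

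A reader might infer more than the documents support:

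- *The skin exception is void at every grade.* It is not: the two catch-alls name only grades 4 and 3, so a grade 5 skin event is outside both.
- *The liver limits are definitely contradicted.* That needs a classification borrowed from dose-modification rules.
- *Part A will escalate on every grade 3 event, with escalation falling to 45% or 18%.* Those figures combine rates found nowhere in the documents with the least likely reading of the trigger.
- *The expansion cohort will close wrongly.* Those figures hold only for an MTD of 200 mg with one final look. Crossing the limit stops dosing at that level, and whether to lower the dose is then for the IRB and the investigator to agree.

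**What to change.** 1. Use *DLT* in every dose rule in Section 9.1 and throughout Table 1, so that the cohort, 70 mg and expansion decisions count the same events.
2. Add to the last DLT item: *other than skin-related events and laboratory abnormalities, which are scored only under the items above*.
3. In the item "Any other Grade 4 adverse event", insert *or higher* after the grade, so that a fatal skin event counts.
4. If the clinical team wants grade 3 skin events counted, delete the skin qualifier from the second item instead. The laboratory part of the added wording is still needed.

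Downside: measured against the literal trigger wording, step 1 stops counting grade 3 cytopenias and most events not attributed to MK-3475 plus radiation, which would loosen Part A escalation. The clinical team should confirm that this is intended, or add to the list the cytopenias it wants counted.

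Apply the single list prospectively. If a cohort has already been scored, report whether its decision would have differed rather than re-scoring it automatically.

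Cost: a wording amendment to the DLT items, the rule text and Table 1, plus one clinical decision on skin, laboratory and cytopenia events. No new data are needed. Later cohorts may expand from 3 to 6 more or less often, within the cap of 40 per part.
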